#### 6.2. Secondary Endpoint(s)

#### 6.2.1. Safety Endpoints

#### 6.2.1.1. Adverse Events

Adverse events will be summarized by treatment and overall and in accordance with sponsor reporting standards using the safety population defined in Section 4.

Incidence and severity of treatment emergent adverse event (TEAE) tables will additionally be produced ('All causality' and 'Treatment related', separately) to summarize the total number of adverse events by preferred term, which will be reported by treatment and overall in accordance with sponsor reporting standards using the safety analysis set defined in Section 4.

The AEs will be presented sorted in descending frequency based on the overall number of AEs (by preferred term or system order class as appropriate) across treatments.

#### 6.2.1.2. Laboratory Data

Laboratory data will be listed and summarized by treatment and overall, in accordance with the sponsor reporting standards using the safety population defined in Section 4. Change from baseline (as defined in Section 3.2.1) summaries will be presented. In summary and listing tables, laboratory abnormalities occurring pre-dose on Day 1 during Periods 2-8, will be attributed to the treatment from the previous Period (e.g., an occurrence pre-dose at Period 3 Day 1, will be attributed to the Period 2 treatment).

## 6.2.1.3. Vital Signs

Absolute values and changes from baseline (as defined in Section 3.2.1) in supine systolic and diastolic blood pressure and pulse rate will be listed, and summarized by treatment and time point, according to sponsor reporting standards using the safety population defined in Section 4.

Mean absolute values and mean changes from baseline for systolic and diastolic blood pressure and pulse rate will be plotted against time point i.e., analysis visit. Corresponding individual plots of changes from baseline will also be produced for each treatment.

Maximum and minimum absolute values and changes from baseline (as defined in Section 3.2.1) for supine vital signs will also be summarized descriptively by treatment using categories as defined in Appendix 2. Numbers and percentages of participants meeting the categorical criteria will be provided. All planned and unplanned post dose time points will be counted in these categorical summaries. All values meeting the criteria of potential clinical concern will be listed. Values meeting the categorical criteria occurring pre-dose on Day 1 during Periods 2-8, will be attributed to the treatment from the previous Period (e.g., an occurrence pre-dose at Period 3 Day 1, will be attributed to the Period 2 treatment).

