### CC

- k. Participants may undergo random urine drug testing at the discretion of the investigator.
- Assessments to be done on Day 1 of Periods 1, 3, and 5 and prior to IP administration on all days indicated.

Table 2. Overall Schedule of Activities Period 6 to ET

Visit Identifier Abbreviations used in this table may be found in Appendix 9			riod 6 81532 only	7)	Perio (PF-070) DI	81532 +	(PF-07	riod 8 7081532 + OSU)	F/U Visit q	F/U Contact Telephone	ET
Day in Study Period a	1-5	6-10	11-15	16-20	1-4	5	1-4	5	7-10	28-35	-
Days in Study b	24-28	29-33	34-38	39-43	44-47	48	49-52	53 f	59-62	80-87	-
Outpatient visit (after ≥10 hr fast)									X		
Physical exam											Χ°
Review contraception use - WOCBP Only (Section 5.3.1)									X	X	
Review drug, alcohol/tobacco use									X		
COVID-19 screening d											
C-SSRS and PHQ-9°	X			X				X	X		X
Review prior or concomitant treatments	$\rightarrow$	$\rightarrow$	$\rightarrow$	$\rightarrow$	_	<del>}</del>	$\rightarrow$	X	X	X	
AE monitoring	→	$\rightarrow$	$\rightarrow$	$\rightarrow$	_	>	$\rightarrow$	X	X	X	
Inpatient stay at CRU	→	$\rightarrow$	$\rightarrow$	$\rightarrow$	_	<del>}</del>	+	Xi			
Body weight g	X		X	X				Xi	X		X
Supine 12-lead ECG		Xh						$X^{i}$			X
Single, supine vital signs assessment	X		X	X				Xi	X		X
Blood Sampling for: k											
- Chemistry	X 			X 				X i	X		X
- Calcitonin, amylase, lipase				$X^1$				Xi			X
- Free T4, TSH, lipid panel, total bile acids								Xi	1		X
- Hematology/HbA1c				X 				Xi	X		X
- Serum pregnancy test m								Xi			
Rosuvastatin administration							Table 4				
DE administration					Table 3						
PF-07081532 administration n	→	→	→	→	1	Table 5	Table 4				
PF-07081532 PK						1					X
Rosuvastatin PK	Χ°						1	Table 4			
Dabigatran PK					Table 3						
CCI											
Urine Sampling for:											
- Urine drug test p											
- Urinalysis (and microscopy, as appropriate)											X

a. Day relative to start of dosing Day 1 of that Period.

b. Day relative to first dose of investigational product (DE) on Day 1 of Period 1.

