# Table 2. Overall Schedule of Activities Period 6 to ET

Visit Identifier Abbreviations used in this table may be found in Appendix 9			riod 6 81532 only	·)	Perio (PF-0708 DF	81532 +	(PF-07	riod 8 7081532 + OSU)	F/U Visit q	F/U Contact Telephone	ET
Day in Study Period a	1-5	6-10	11-15	16-20	1-4	5	1-4	5	7-10	28-35	-
Days in Study b	24-28	29-33	34-38	39-43	44-47	48	49-52	53 f	59-62	80-87	-

- c. Brief exam if findings during previous exam or new/open AEs, if appropriate, at investigator discretion.
- d. Participants will be screened for COVID-19 according to local practice prior to being admitted to the clinic for confinement in Period 1. A subsequent test will be done according to local procedure if participants develop COVID-19 like symptoms. See also Section 8.3.5 (COVID-19 Specific Assessments). If participants test positive for SARS-CoV-2 infection, they will be discharged from the study.
- e. C-SSRS and PHQ-9 will be administered in Period 6 on Days 5 and 19, and in Period 8 on Day 5 (discharge from CRU).
- f. Discharge from CRU.
- g. Body weight to be obtained on Days 5, 12 and 19 in Period 6.
- h. ECG to be obtained on Day 10 of Period 6.
- i. Assessments to be obtained on Day 5 of Period 8 prior to D/C from the CRU.
- j. Includes BP and PR predose; to be obtained on Days 5, 12 and 19 in Period 6.
- k. Collection following fasting duration specified in Section 5.3.2.
- 1. Chemistry to be obtained on Days 1 and 20 in Period 6; calcitonin, amylase, lipase and hematology to be obtained on Day 20 in Period 6.
- m. Serum β-hCG for all WOCBP
- n. Dosing to occur QD with breakfast. Note that there is no PF-07081532 administration on Study Day 53 or anytime thereafter.
- o. The rosuvastatin PK sample is to be collected predose (0 hr) on Day 1 of Period 6.
- p. Participants may undergo random urine drug testing at the discretion of the investigator.
- q. The follow-up visit 7-10 days after the last dose of study intervention (Period 8, Day 4) can be on-site or via telephone call. Whether the follow-up visit is on-site or via telephone call is at the discretion of the Investigator. Regardless of location (ie, on site or telephone call), contraception use, drug, alcohol/tobacco use, concomitant medications and AEs must be reviewed/assessed as appropriate.

Table 3. Schedule of Activities – Period 1 (DE ONLY), Period 4 (DE + PF-07081532 80 mg QD) and Period 7 (DE + PF-07081532 260 mg QD)

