#### 5.2. General Methods

Unless otherwise stated, all summaries and plots will be presented by treatment group (equivalent to 'by Period'). The following treatment labels (or similar) will be used, which represent Periods 1 to 8 as:

Period	Treatment Label
1	Dabigatran etexilate 150 mg (Period 1)
2	Rosuvastatin 10 mg (Period 2)
3	PF-07081532 titration up to 40 mg QD (Period 3)
4	PF-07081532 80 mg QD + dabigatran etexilate 150 mg (Period 4)
5	PF-07081532 80 mg QD + rosuvastatin 10 mg (Period 5)
6	PF-07081532 titration up to 240 mg QD (Period 6)
7	PF-07081532 240 mg QD + dabigatran etexilate 150 mg (Period 7)
8	PF-07081532 240 mg QD + rosuvastatin 10 mg (Period 8)

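### The per-period vital-sign abnormality percentages in SAP 6.2.1.3 are not comparable across periods, because scheduled post-dose readings range from none to three per period

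*SAP*

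**What the plan says.** SAP 6.2.1.3 takes each participant's highest and lowest readings, and largest changes from baseline. These extremes "for supine vital signs will also be summarized descriptively by treatment using categories as defined in Appendix 2". Which readings count is stated without any limit on number: "Numbers and percentages of participants meeting the categorical criteria will be provided. All planned and unplanned post dose time points will be counted in these" summaries.

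The columns are study periods. SAP 5.2 says "all summaries and plots will be presented by treatment group (equivalent to 'by Period"), and lists eight labels that run up the PF-07081532 dose ladder.

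The readings come from the protocol's Schedule of Activities:

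- Table 1, footnote l: "Assessments to be done on Day 1 of Periods 1, 3, and 5 and prior to IP administration on all days indicated". The vital-signs row of that table also marks Period 3 Day 8.
- Table 2, footnote j: "Includes BP and PR predose; to be obtained on Days 5, 12 and 19 in Period 6".
- Table 2, footnote i: "Assessments to be obtained on Day 5 of Period 8 prior to D/C from the CRU".
- Table 2, footnote q: "The follow-up visit 7-10 days after the last dose of study intervention (Period 8, Day 4) can be on-site or via telephone call". Vital signs are marked at this visit and at early termination.

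Two SAP rules decide where a reading goes. Section 3.2.1 makes the last pre-dose value in Period 1 the baseline. Section 6.2.1.3 assigns a qualifying pre-dose value on Day 1 of Periods 2 to 8 to the preceding period. The section names the safety population but gives no denominator for a period in which no reading was taken.

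**The concern.** The chance that the worst of several readings crosses a fixed limit grows with the number of readings. Here a worst-of-three percentage for Period 6 stands beside worst-of-one percentages for Periods 2, 3, 4 and 8, and beside Periods 1, 5 and 7, for which nothing was scheduled after dosing. Unplanned readings are added on top.

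Because the columns are also the dose ladder, a reader will tend to look along them for a trend. The protocol synopsis names changes in heart rate and blood pressure as a potential risk of PF-07081532, and vital signs are a secondary endpoint. With no change in the underlying distribution, the table could show a rise in Period 6, nothing in Period 7 and a lower figure in Period 8. That looks like a titration effect that settles at constant dose.

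**Working it through.** The documents give no abnormality rate or expected count for this table, so there is no stated figure to reproduce.

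**Step 1: count the scheduled readings.** The inputs are Protocol Tables 1 and 2 with footnotes i, j, l and q, the baseline definition in SAP 3.2.1, and the Day 1 pre-dose rule in SAP 6.2.1.3. That rule is worded for values that meet a criterion; I apply it to the reading itself.

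| Period | Readings as printed | Post-dose readings after SAP rules |
|---|---|---|
| 1 | Day 1 (baseline) | 0 |
| 2 | none | 1 (Period 3 Day 1) |
| 3 | Days 1 and 8 | 1 (Day 8) |
| 4 | none | 1 (Period 5 Day 1) |
| 5 | Day 1 | 0 |
| 6 | Days 5, 12 and 19 | 3 |
| 7 | none | 0 |
| 8 | Day 5 | 1, or 2 with an on-site follow-up reading |

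The second figure for Period 8 depends on an attribution that the SAP does not settle for vital signs. Its rule on follow-up (Section 3.2.1) is written for events.

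**Step 2: chance of at least one crossing in k readings.** Let p be the chance per reading and ρ the correlation between readings in one participant. Neither is in the documents. I assume p from 1% to 10% and ρ from 0 to 1, with no drug effect.

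- Independent readings: 1 − (1 − p)^k. For p = 5% and k = 3, this is 1 − 0.95³ = 14.3%.
- Correlated readings (exchangeable normal model): 1 − ∫ Φ((t − √ρ·x)/√(1 − ρ))^k φ(x) dx, with t = Φ⁻¹(1 − p), integrated numerically.

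Three readings, with the ratio to one reading in brackets:

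| p | ρ = 0 | ρ = 0.5 | ρ = 0.9 |
|---|---|---|---|
| 1% | 2.97% (2.97) | 2.65% (2.65) | 1.77% (1.77) |
| 2% | 5.88% (2.94) | 5.10% (2.55) | 3.40% (1.70) |
| 5% | 14.26% (2.85) | 11.84% (2.37) | 7.95% (1.59) |
| 10% | 27.10% (2.71) | 21.84% (2.18) | 14.99% (1.50) |

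At ρ = 1 the ratio is 1.

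**Step 3: in participants.** With about 24 enrolled and p = 5%, one reading gives 24 × 0.05 = 1.2 expected participants. Three readings give 24 × 0.1426 = 3.4 if independent and 24 × 0.1184 = 2.8 at ρ = 0.5. At p = 2% and ρ = 0.5 the figures are 0.5 and 1.2.

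**Step 4: against a two-reading Period 8.** At p = 5% and ρ = 0.5, two readings give 8.78%. The ratio of Period 6 to Period 8 is then 11.84/8.78 = 1.35. If instead Period 6 lost a reading when the study was shortened, two readings against one give 8.78/5 = 1.76.

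**Step 5: columns with no reading.** For Periods 1, 5 and 7, k = 0. Unless an unplanned or early-termination reading falls there, the count is zero whatever the drug does. If the safety population is the denominator, the table prints 0%.

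**The case against.** The strongest reply is that the plan already shows the data in other ways. SAP 6.2.1.3 summarizes values and changes by treatment and time point, plots means by visit, plots individual changes, and lists every value of potential clinical concern. With about 24 participants, a reader can find which day produced each crossing. The SAP also sets no hypothesis tests or decision rules (Section 5.1), and nothing in it assigns the categorical table to dose comparison. This stands, and it confines the harm to one descriptive secondary table. It does not remove the point: the by-time-point summaries are of continuous values, and the listing gives no rates, so the Appendix 2 percentages appear only by period.

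A second reply is that crossings may be rare. The pulse limits are absolute (below 40 or above 120 bpm), the upper blood pressure limits are 200 and 100 mm Hg in participants screened below 140/90, and changes from a shared baseline are more highly correlated. This also stands as a limit on size. It pulls the ratio towards the lower end for the change criteria and makes the gap in participants small for the absolute ones.

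A reader might go further and infer that the Period 6 column is inflated by the schedule rather than by the drug, or that it is firmly two to three times too high. The documents support neither. By Protocol Table 8, the Period 6 readings fall at the step from 120 to 160 mg (Day 5, pre-dose), at 200 mg (Day 12) and at 240 mg (Day 19), over 20 days. Schedule, dose and time are confounded, so the schedule can raise the column but a drug effect cannot be excluded. The multiple depends on assumed inputs and is smaller against a two-reading Period 8.

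**Conclusion.** The point holds as one of comparability. As printed, the per-period percentages rest on 0, 1, 1, 1, 0, 3, 0 and 1 scheduled post-dose readings, with Period 8 possibly 2, and SAP 6.2.1.3 makes no allowance for this. The schedule alone can raise Period 6 to about 1.5 to 3 times a one-reading period, for assumed per-reading rates of 1% to 10% and correlation up to 0.9. A zero in Period 1, 5 or 7 is not evidence that nothing happened.

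One limit applies to the counts themselves. SAP 2.1 says the study was shortened by 6 days after the 240 mg cap and that the printed design is no longer current, but it gives no revised schedule. The counts should be confirmed against the schedule actually run. This is a minor improvement to one secondary safety table; no primary PK result depends on it.

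**What to change.** In SAP 6.2.1.3, tabulate the Appendix 2 vital-sign categories at each scheduled time point, using planned readings only and the number of participants measured as denominator. As printed, these are Period 3 Days 1 and 8, Period 5 Day 1, Period 6 Days 5, 12 and 19, Period 8 Day 5, and the follow-up visit where done on site. Name this as the table for any comparison between periods.

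Keep the worst-value-per-period table as a screen, with these additions:

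- show the planned readings and the participants assessed in each column;
- mark periods with no scheduled post-dose reading as *not assessed* rather than 0%;
- list unplanned values separately;
- state which column receives follow-up and early-termination readings;
- take the counts from the schedule as executed.

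The cost is one longer table and a wording change, using data already collected. The new table equalizes the number of readings behind each percentage. It does not separate dose from time in a fixed-sequence design, and it cannot supply readings for Periods 1, 5 and 7.

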# 6.2.1.4. Electrocardiogram (ECG)

Absolute values and changes from baseline (as defined in Section 3.2.1) in QT interval, heart rate, QTcF interval, PR interval and QRS interval will be listed, and summarized by treatment and time point using sponsor reporting standards using the safety population defined in Section 4. Tables will be paged by parameter.

Mean changes from baseline for QT interval, heart rate and QTcF interval will be plotted against time point i.e., analysis visit. Corresponding individual plots of changes from baseline will also be produced for each treatment.

Maximum absolute values and changes from baseline for QTcF, PR and QRS will also be summarized descriptively by treatment using categories as defined in Appendix 2. Numbers and percentages of participants meeting the categorical criteria will be provided. All planned and unplanned post dose timepoints will be counted in these categorical summaries. All values meeting the criteria of potential clinical concern will be listed. Values meeting the categorical criteria occurring pre-dose on Day 1 during Periods 2-8, will be attributed to the

> DMB02-GSOP-RF02 7.0 Statistical Analysis Plan Template 31-Jan-2022 PFIZER CONFIDENTIAL TMF Doc ID: 98.03 Page 20 of 30

treatment from the previous Period (e.g., an occurrence pre-dose at Period 3 Day 1, will be attributed to the Period 2 treatment).

#### 6.2.1.5. Additional Safety Endpoints of Interest

Absolute values and changes from baseline for body weight (both absolute and percent change, separately), fasting glucose and HbA1c will summarized by treatment and time point as outlined in Section 5.2.1 for participants in the safety population (as defined in Section 4).

#### 6.2.1.6. C-SSRS

Baseline and post-baseline C-SSRS data (mapped to C-CASA scores as described in Section 3.2.2.1) using the safety population defined in Section 4 will be summarized categorically by treatment and time point as outlined in Section 5.2.2.

## 6.2.1.7. PHQ-9

Baseline and post-baseline PHQ-9 data (responses to each of the 9 items) using the safety population defined in Section 4, will be summarized categorically for each question separately by treatment and time point as outlined in Section 5.2.2.

The PHQ-9 total score as defined in Section 3.2.2.2 will additionally be summarized descriptively by treatment group and time point as outlined in Section 5.2.1.

## 6.2.1.8. Mental Health Risk Assessment

The number of participants who met the criteria for referral to a mental health professional will be listed and summarized by treatment group and time point as outlined in Section 5.2.2.

# 6.2.2. Additional Plasma PK Parameters

#### 6.2.2.1. Additional Plasma PK Parameters for Total Dabigatran and Rosuvastatin

 $C_{max}$ ,  $T_{max}$ , CL/F,  $V_z/F$ ,  $t_{\frac{1}{2}}$  for total dabigatran and rosuvastatin alone and co-administered with PF-07081532 will be listed, summarized descriptively and analyzed by treatment for participants in the PK Parameter Set (as defined in Section 4). Missing values will be handled as detailed in Section 5.3.

 $C_{max}$ ,  $T_{max}$ , CL/F,  $V_z/F$ ,  $t_{\frac{1}{2}}$  will be summarized for each treatment (total dabigatran and rosuvastatin will be reported in separate tables) as specified in the table below:

Parameter	Summary Statistics
C max , CL/F, V z /F N, arithmetic mean, median, cv%, standard devia	
	minimum, maximum, geometric mean and geometric
	cv%.
T max	N, median, minimum, maximum.
t 1/2	N, arithmetic mean, median, cv%, standard deviation,
	minimum, maximum.

# Table 8. Summary statistics to be produced for additional plasma PK Parameters for total dabigatran and rosuvastatin

Natural  $log_e$  transformed  $C_{max}$  of total dabigatran administered without PF-07081532 on Period 1 or coadministered with PF-07081532 in Period 4 and on Period 7 will be analyzed using a mixed effect model as described in Section 5.2.3.

The 2 test treatments will be 'dabigatran and PF-07081532 80 mg QD' (Period 4) and 'dabigatran and PF-07081532 240 mg QD' (Period 7), which will be reported separately in comparison to the reference treatment of 'dabigatran without PF-07081532' (Period 1).

Natural  $log_e$  transformed  $C_{max}$  of rosuvastatin administered alone in Period 2 or coadministered with PF-07081532 on Period 5 and Period 8 will be analyzed and reported separately using the same mixed effect model as described above for total dabigatran. The 2 test treatments will be 'rosuvastatin and PF-07081532 80 mg QD' (Period 5) and 'rosuvastatin and PF-07081532 240 mg QD' (Period 8), which will be reported separately in comparison to the reference treatment of 'rosuvastatin without PF-07081532' (Period 2).

The following plots will be presented:

 Box and whisker plots for individual Cmax will be presented by treatment and overlaid with geometric means. These will be produced for total dabigatran and rosuvastatin Cmax separately.

# 6.2.2.2. Plasma PK Parameters for PF-07081532

Plasma PK parameters for PF-07081532 as described in Section 3.2.4 will be listed and summarized descriptively for participants in the PK Parameter Set (as defined in Section 4). Missing values will be handled as detailed in Section 5.3.

AUC24,  $C_{max}$ ,  $T_{max}$  will be summarized for each treatment period of PF-07081532 as required in the table below:

Parameter	Summary Statistics
AUC 24 , C max	N, arithmetic mean, median, cv%, standard deviation, minimum, maximum, geometric mean and geometric cv%.
T max	N, median, minimum, maximum.
DMB02-GSOP-RF02 7.0 Statistical Analysis Plan Template 31-Jan-2022	
PFIZER CONFIDENTIAL	
TMF Doc ID: 98.03	
Page 22 of 30	

#### Table 9. Summary statistics to be produced for plasma PK Parameters for PF-07081532

The following plots will be presented:

Box and whisker plots for individual PK parameters of PF-07081532 (AUC24 and Cmax) will be presented by treatment and overlaid with geometric means.

The following summaries will additionally be presented for the plasma concentration data of PF-07081532 using the PK Concentration Set (as defined in Section 4):

[figure not shown]
- a listing of all concentrations sorted by participant ID and nominal time post-dose for each PF-07081532 treatment period separately. The concentration listing will also include the actual times. Deviations from the nominal time will be given in a separate listing.
- a summary of concentrations by each nominal time post-dose (produced separately for each treatment period), where the set of statistics will include n, mean, median, standard deviation, coefficient of variation (CV), minimum, maximum and the number of concentrations above the lower limit of quantification.
- median concentration time plots (on both linear and semi-log scales) against nominal time post-dose by treatment period. One plot for each scale will be presented which will include both PF-07081532 treatment periods in the same plot.
- individual concentration time plots by treatment period (on both linear and semi-log scales) against actual time post-dose (there will be separate spaghetti plots for each treatment period, with a line for each participant per scale).
- individual concentration time plots by participant (on both linear and semi-log scales) against actual time post-dose. One plot for each participant and scale will be presented, which will include both PF-07081532 treatment periods in the same plot.

For summary statistics and median plots by sampling time, the nominal PK sampling time will be used. For individual participant plots by time, the actual PK sampling time will be used. Median profiles will be presented on both linear-linear and log-linear scales.

